9.4.5 Baseline Descriptive Statistics

Demographics and other baseline characteristics will be presented by treatment group and with both treatment groups combined. For continuous baseline variables, percentiles (median, 25th and 75th), means and standard deviations will be presented. For categorical baseline variables, frequencies and percentages will be presented.

Since randomization is expected to produce balance between treatment groups with respect to baseline characteristics, inferential statistics to compare the two treatment groups on baseline characteristics are not recommended, and will not be used.

9.4.6 Planned Interim Analyses

No interim analysis is planned.

9.4.7 Sub-Group Analyses

Per NIH policy, sex differences will be statistically tested. It is expected however that this subgroup analysis will be underpowered to detect sex differences.

9.4.8 Tabulation of Individual Participant Data

Individual participant data will be listed by measure and time point.

9.4.9 Exploratory Analyses

An exploratory endpoint for this study is the clinical outcomes, cardiorespiratory function, cognition, biomarkers, metabolomics, ultrasound-based muscle measurements, and vascular and autonomic function. An analysis of covariance (ANCOVA) will be used for objective #4, with the variables of interest after the 10-week intervention (study visit 2) as the dependent variable, baseline variables (study visit 1) as the covariate and treatment group as the fixed factor. Other factors related to participant characteristics such as timing (e.g., early vs. late study entry) and those related to COVID-19 severity (e.g., age, comorbidities, hospital admission, duration of hospitalization, ventilator use, drug treatments, etc.) may have potential effects on exploratory outcomes and may be included as covariates in the model. The association between these baseline (i.e., pre-randomization) patient characteristics and exploratory outcomes will be tested in bivariate and multivariable analyses, and the optimal set of predictors will be included in the final model to account for baseline participant characteristics that may affect recovery.

We are also interested in the feasibility of conducting the AET program remotely in participants recovering from COVID-19 that were randomized to the CON arm (objective #5). Outcomes related to feasibility such as retention, safety, exercise adherence and participant experience will be reported. A paired samples t-test will be used to examine changes in variables of interest (Study Visit 2 and 3) in those participants that participated in remote exercise monitoring.

We are also interested in examining relationships between various outcomes (functional, physiological variables, health outcome variables, etc.) on longer-term follow-up. Therefore, we will explore (objective #6) relationships between physiological variables and post-study health outcome variables obtained during the 1 year follow-up period. These will be analyzed using Pearson product moment correlations and appropriate nonparametric procedures.

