1 PROTOCOL SUMMARY

1.1 SYNOPSIS

- Title:** COVID-19, Chronic Adaptation and Response to Exercise (COVID-CARE): A Randomized Controlled Trial
- Study Description:** This randomized controlled trial will determine whether aerobic exercise training has a beneficial effect on physical function, health-related quality of life, free-living physical activity and sleep quality among survivors of COVID-19. Participants will be randomized to either an aerobic exercise training and education (AET+) group or a control education only group (CON) for 10 weeks. Assessments for physical function, self-reported health outcomes for quality of life (QOL), free-living physical activity and sleep quality will be measured at baseline and following the 10-week intervention period. Participants in the CON group will then crossover and perform AET after the 10-week follow-up visit. All participants will be monitored for one year to capture free-living physical activity, sleep quality and health-related QOL outcomes over time. It is hypothesized that following 10 weeks, physical function, health-related QOL, free-living physical activity and sleep quality will show greater improvement with AET+.
- Objectives:** Primary Objective: To examine the effect of aerobic exercise training on physical function in participants recovering from COVID-19.
- Secondary Objectives: To examine the effect of aerobic exercise training on patient reported outcomes and other health-related QOL components in participants recovering from COVID-19; To examine the effect of aerobic exercise training on free-living physical activity and sleep quality in participants recovering from COVID-19.
- Exploratory Objectives: To explore the effect of aerobic exercise training on clinical outcomes, cardiorespiratory function, cognition, biomarkers, metabolomics, ultrasound-based muscle measurements, and vascular function in participants recovering from COVID-19; To explore the feasibility of conducting the AET program remotely in the crossover CON group of participants recovering from COVID-19; To explore follow-up physical activity, sleep quality and health-related QOL outcomes over 1 year in participants recovering from COVID-19.
- Endpoints:** Primary Endpoints: Physical function as measured by distance walked during the 6 minute walk test after 10 weeks post-randomization with AET+ and CON.

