- Secondary Endpoints: Patient-reported outcomes and other health-related components after 10 weeks post-randomization with AET+ and CON; Free-living physical activity and sleep quality after 10 weeks post-randomization with AET+ and CON.
- Exploratory Endpoints: Clinical outcomes, cardiorespiratory function, cognition, biomarkers, metabolomics, ultrasound-based muscle measurements, and vascular function after 10 weeks post-randomization with AET+ and CON; Collection of initial feasibility data to conduct exercise sessions remotely; Explore relationships between the physiological variables and post-study health outcome variables over time.

Abbreviated Title: Exercise and COVID-19**Version Date: 3/18/2025**

Study Population: Ninety male and female adults (18 to 80 years old) recovering from COVID-19, from the greater Washington DC metropolitan area.

Phase: N/A

Description of Sites/Facilities Single-site study (NIH Clinical Center)

Enrolling Participants:

[figure not shown]
Description of Study Intervention: Aerobic Exercise Training: Participants will perform aerobic exercise, 3 times a week for 10 weeks, with supervision by credentialed RMD staff members. Participants will be encouraged to target 30 minutes of continuous aerobic exercise. The intensity of exercise will be gradually increased from light-moderate to moderate-high as safely tolerated by the participant and guided using heart rate targets.
Education: Participants will have weekly education sessions for 10 weeks. All sessions are ~1 hour and will be conducted remotely by credentialed RMD staff members.

Participants randomized to AET+ will perform both exercise training and education during the 10 week intervention period. Participants randomized to CON will perform education only during the first 10 weeks, followed by exercise training during the second 10 weeks (crossover).

Study Duration: 36 months

Participant Duration: Up to 17 months if randomized to AET+, and up to 21 months if randomized to CON

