#5. Explore the feasibility of conducting the AET program remotely in participants recovering from COVID-19 that were randomized to the CON arm	Measure retention, safety, exercise adherence and participant experience in the CON group that crossed over to exercise.	Collection of data to examine feasibility of conducting exercise sessions remotely in this population. It is expected that remotely conducted exercise sessions will be feasible based on effectiveness of remotely conducted pulmonary rehabilitation in patients with chronic obstructive pulmonary disease (78).
#6. Explore follow-up free-living physical activity,	Free-living physical activity, sleep quality, and health-	There are currently no studies available for changes in physical

Abbreviated Title: Exercise and COVID-19

[figure not shown]
Version Date: 3/18/2025

OBJECTIVES	ENDPOINTS	JUSTIFICATION FOR ENDPOINTS
sleep quality, patient reported outcomes and other health-related QoL components in participants recovering from COVID-19	related QOL are measured every 3 months for 1 year in both groups.	activity, sleep quality and QOL after COVID-19 over an extended period of time. It is expected that benefits from exercise training will be maintained at 1-year follow-up, based on long-term studies in patients with lung disease following PR programs (79 , 80).

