9.4.3 Analysis of the Secondary Endpoints

A secondary endpoint for this study is the patient-reported outcomes and other health-related components, as well as free living physical activity and sleep quality. An analysis of covariance (ANCOVA) will be used for objective #2 and #3, with the variables of interest after the 10-week intervention (study visit 2) as the dependent variable, baseline variables (study visit 1) as the covariate and treatment group as the fixed factor. Other factors related to participant characteristics such as timing (e.g., early vs. late study entry) and those related to COVID-19 severity (e.g., age, comorbidities, hospital admission, duration of hospitalization, ventilator use, drug treatments, etc.) may have potential effects on secondary outcomes and may be included as covariates in the model. The association between these baseline (i.e., pre-randomization) patient characteristics and secondary outcomes will be tested in bivariate and multivariable analyses,

and the optimal set of predictors will be included in the final model to account for baseline participant characteristics that may affect recovery.

Analyses of secondary endpoints are not dependent on findings of the primary endpoints.

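### Objective 6 follows activity, sleep and quality of life for a year, but the only inferential analysis named for it is correlation, which cannot estimate whether scores were maintained

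*Combined protocol and SAP*

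**What the plan says.** The synopsis (1.1) gives the exploratory objective as "To explore follow-up physical activity, sleep quality and health-related QOL outcomes over 1 year in participants recovering from COVID-19". The objectives table (Section 3, Objective 6) specifies that activity, sleep quality and health-"related QOL are measured every 3 months for 1 year in both groups", and its justification column adds "It is expected that benefits from exercise training will be maintained at 1-year follow-up".

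The analysis text tagged to Objective 6 in Section 9.4.9 has a different target: "relationships between physiological variables and post-study health outcome variables obtained during the 1 year follow-up period". The method follows: "These will be analyzed using Pearson product moment correlations and appropriate nonparametric procedures". The matching exploratory endpoint in the synopsis is also about association: "Explore relationships between the physiological variables and post-study health outcome variables over time".

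The objective and its endpoints therefore concern levels over a year, while the analysis concerns associations between variables.

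**The concern.** Whether scores hold up after training ends is a question about mean change. Correlation measures how participants rank or scatter relative to one another and carries no information about a shift in the group mean. If every participant lost the whole training gain, the planned coefficients would be the same as if nobody had lost anything.

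Each participant is asked for four follow-ups after the last study visit. Without a named contrast, any statement about the year would rest on an analysis chosen after the data are seen, or on a correlation read as if it spoke to durability.

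**Working it through.** **1. Does another section analyse the follow-up data?**

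| Section | What it covers | Uses months 3 to 12? |
|---|---|---|
| 9.4.1 General Approach | Means with SD; no change score or time contrast named | Possibly, as description only |
| 9.4.2 Primary | ANCOVA of 6MWT distance at Visit 2 | No |
| 9.4.3 Secondary | ANCOVA "with the variables of interest after the 10-week intervention (study visit 2) as the dependent variable" | No |
| 9.4.8 Tabulation | Listing of individual data | Listing only |
| 9.4.9, Objective 4 | ANCOVA at Visit 2 | No |
| 9.4.9, Objective 5 | Paired t-test, Visits 2 and 3, remote exercisers | No |
| 9.4.9, Objective 6 | Correlations and unspecified nonparametric procedures | Yes, for relationships |

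The endpoint column for Objectives 2 and 3 also lists the 3-monthly measurements, but Sections 9.1 and 9.4.3 confine those analyses to Visit 2. No section defines a change from end of training, a longitudinal model or a criterion for maintenance.

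**2. What correlation can show.** For any constant c,

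corr(X, Y − c) = cov(X, Y − c) / [SD(X) · SD(Y − c)] = cov(X, Y) / [SD(X) · SD(Y)] = corr(X, Y).

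Ranks are also unchanged, so Spearman's coefficient behaves in the same way. This is an identity and depends on no trial figure.

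An illustration with assumed values: n = 76, end-of-training SD about 10, training gain 5 points, follow-up noise SD 4. The 12-month scores were shifted by a common amount.

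| Case | Shift | Pearson (physiological variable, 12 months) | Spearman | Mean change from end of training (95% CI) |
|---|---|---|---|---|
| Kept | 0 | 0.1546 | 0.1193 | −0.3 (−1.2 to 0.6) |
| Half lost | −2.5 | 0.1546 | 0.1193 | −2.8 (−3.7 to −1.9) |
| All lost | −5 | 0.1546 | 0.1193 | −5.3 (−6.2 to −4.4) |
| Worse than before training | −10 | 0.1546 | 0.1193 | −10.3 (−11.2 to −9.4) |

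The correlation between end-of-training and 12-month scores was also the same in all four cases (0.9149). Only the within-person change separates them.

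**3. Precision available for a change.** For a simple paired change, the 95% CI half-width in units of the SD of the change is t(0.975, n − 1)/√n.

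- n = 76: 1.992/8.718 = 0.229.
- n = 50: 2.010/7.071 = 0.284.

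The 76 is the Section 9.2 target for completing Visit 2, not a projected number at 12 months. The 50 is assumed, to show the effect of attrition. These figures are a guide; they are not the precision of the mixed model itself.

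**4. Do the two arms' schedules line up?** From the Schedule of Activities (1.3), in nominal weeks after end of training:

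- AET+ (Visit 2 at week 14): 30 − 14 = 16, 43 − 14 = 29, 56 − 14 = 42, 69 − 14 = 55.
- CON (Visit 3 at week 29): 45 − 29 = 16, 58 − 29 = 29, 71 − 29 = 42, 84 − 29 = 55.

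The spacing is identical, so time since end of training is a workable axis for both arms.

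**The case against.** The best defence is that correlation suits the aim Section 9.4.9 sets itself. Section 9.1 states hypotheses only for Objectives 1 to 3. Objective 6 is exploratory, and the expectation of maintenance stands in a justification column. This is right: a reader might infer that maintenance is a formal hypothesis the plan fails to test, and the documents do not support that. What stands is the narrower mismatch: the objective and endpoints concern outcomes over a year, and the analysis does not.

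Three further stronger readings also go too far.

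- **That correlation is all that will be reported.** Section 9.4.1 allows means and SDs, which could show a fall if tabulated by time point. The undefined nonparametric procedures most naturally mean rank correlation, given the preceding sentence about relationships, but a test of change is not strictly excluded. What is missing is a named contrast over time.
- **That the repeated follow-ups are pooled as if independent.** Section 9.4.9 does not say how up to four values per participant enter the correlations. Separate coefficients at each time point would fit the text equally well. The handling is unspecified.
- **That a better model would show whether a training benefit was kept.** CON participants cross over to exercise after Visit 2, and Section 4.2 says that spontaneous recovery is poorly understood. Any model can show persistence of scores but cannot attribute it to training.

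**Conclusion.** The point holds in this limited form. As written, the plan names no analysis that estimates whether activity, sleep or quality-of-life scores were maintained from the end of training to 12 months. The only inferential method named for Objective 6 cannot do so, by an identity that needs no assumption.

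The consequence is confined to what can be said about the follow-up year. The primary comparison, the Visit 2 secondary comparisons and the sample size are untouched. The 6MWT is not scheduled at the 3-month follow-ups, so its persistence over that year cannot be assessed by any method.

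The precision figures (about 0.23 SD of the change at 76, 0.28 at 50) assume that those numbers are followed to 12 months. They suggest a usable estimate is feasible; they do not predict the trial's actual precision.

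**What to change.** In Section 9.4.9, make the main Objective 6 analysis a linear mixed model for repeated measures, for each outcome that has a pre-training value and is collected during follow-up. This leaves out the PGIC, which is not given at baseline (8.3.6.13), and the VAS-CFS, which is not collected during the follow-up year (8.3.6.6).

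- **Time levels:** pre-training (Visit 1 for AET+, Visit 2 for CON); end of training (Visit 2 for AET+, Visit 3 for CON); then +3, +6, +9 and +12 months. Pre-training must be a modelled time level, not only a covariate, so that change from it can be estimated.
- **Other terms:** arm/sequence as a fixed effect and participant as a random effect.
- **Report:** mean change with 95% CI from end of training to 12 months and from pre-training to 12 months.
- **Accelerometer:** the device is worn continuously through training (8.3.9), so define the end-of-training window so that supervised sessions do not count as free-living activity.
- **Interpretation:** state that no untrained control exists after Visit 2, so the result describes within-participant persistence of scores, not a retained causal effect of training.
- **Correlations:** keep them as a supplement, calculated separately at each time point.

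The follow-up data are already scheduled, so nothing new is collected. The cost is added wording in the analysis section and some extra exploratory analysis across several questionnaires.

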10 REGULATORY AND OPERATIONAL CONSIDERATIONS

10.1 INFORMED CONSENT PROCESS

10.1.1 Consent Procedures and Documentation

The informed consent document will be provided as a physical or electronic document to the participant for review prior to consenting. All participants will receive a verbal explanation in terms suited to their comprehension of the purposes, procedures and potential risks of the study and of their rights as research participants. Participants will have the opportunity to carefully review the consent form and ask questions regarding this study prior to signing.

A signed consent document will be obtained before any study procedures are conducted. Only study investigators designated as able to obtain consent, will obtain informed consent. All study investigators obtaining informed consent will have completed the NIMH Human Subjects Protection Unit (HSPU) “Elements of Successful Informed Consent” training.

If the investigator feels the individual’s capacity to consent to research participation is questionable, the NIH HSPU will be requested to determine whether the individual has the capacity to provide consent. If the individual is determined to not have the capacity to provide consent to research, they will not participate in the study.

The consent form contains all required elements and will be used for all participants. The initial consent process as well as re-consent, when required, will take place in person or remotely (e.g., via telephone or other NIH approved remote platforms used in compliance with policy, including HRPP Policy 303) per discretion of the designated study investigator and with the agreement of the participant. Whether in person or remote, the privacy of the subject will be maintained. Consenting investigators (and participant, when in person) will be located in a private area (e.g., clinic consult room). When consent is conducted remotely, the participant will be informed of the private nature of the discussion and will be encouraged to relocate to a more private setting if needed. If the consent process is occurring remotely, participants and investigators may view individual copies of the approved consent document on screens at their respective locations, or the same screen may be used when both the investigator and the participant are co-located but this is not required. If required, the witness signature will be obtained similarly as described for the investigator and participant below.

Consent will be documented with required signatures on the physical document (which includes the printout of an electronic document sent to the participant) or on the electronic document. The process for documenting signatures on an electronic document is described below.

When a hand signature on an electronic document is used for the documentation of consent, this study will use the iMedConsent platform (which is 21 CFR Part 11 compliant) to obtain the required signatures. Both the investigator and the participant will sign the electronic document

using a finger, stylus or mouse. Electronic signatures (i.e., the “signature” and a timestamp are digitally generated) will not be used.

10.1.2 Considerations for Consent of NIH staff, or family members of study team members

If the potential participant is a member of the research team where this research is taking place, procedures outlined in NIH HRPP Policy 404 will be followed. Consent for NIH staff will be obtained as detailed above with the following additional protections:

Consent from staff members will be obtained by an individual independent of the staff member’s team whenever possible. Otherwise, the consent procedure will be independently monitored by the CC Department of Bioethics Consultation Service to minimize the risk of undue pressure on the staff member.

10.1.3 Consent of Adults who lack, or lose, decision-making capacity to consent to research participation

Adults unable to consent to research are excluded from enrolling in the protocol. However, it is possible that participants enrolled in the protocol may permanently lose the capacity to consent for themselves during the course of the study. In the event this occurs, participants will be withdrawn from the study.

The PI or AI will contact the NIH Ability to Consent Assessment Team (ACAT) for evaluation as needed for an independent assessment of whether an individual has the decision-making capacity to provide consent to research participation.

10.2 STUDY DISCONTINUATION AND CLOSURE

This study may be temporarily suspended or prematurely terminated if there is sufficient reasonable cause. If the study is prematurely terminated or suspended, the PI will promptly inform study participants, the IRB, and Clinical Director, and will provide the reason(s) for the termination or suspension. Study participants will be contacted, as applicable, and be informed of changes to the study visit schedule.

Circumstances that may warrant termination or suspension include, but are not limited to:

- Determination of unexpected, significant, or unacceptable risk to participants
- Demonstration of efficacy that would warrant stopping
- Insufficient compliance to protocol requirements
- Data that are not sufficiently complete and/or evaluable
- Determination that the primary endpoint has been met
- Determination of futility

Study may resume once concerns about safety, protocol compliance, and data quality are addressed, and satisfy the IRB.

